3. PATIENT ELIGIBILITY

3.1 Inclusion Criteria

Patients with histologically documented local-regional recurrent squamous cell carcinoma of the head and neck, or second primary squamous cell carcinoma of the head and neck;

Patients must be willing to undergo research biopsy for tissue collection at baseline and at disease progression;

Previous receipt of at least 30 Gy of radiation for HNSCC with overlapping fields;

Not eligible or poor candidate or patient refusal of surgery for recurrence;

Evaluable disease apparent on imaging (MRI or CT);

1 to 3 sites of recurrence (<60 cm³ per site, total volume <100 cm³);

Age ≥ 18 years;

Eastern Cooperative Oncology Group (ECOG) = 0, 1, or 2;

Adequate hematologic function defined as follows:

WBC ≥ 2000/µL;

Absolute neutrophil count (ANC) ≥ 1,500 cells/mm³;

Platelets ≥ 100,000 cells/mm³;

Hemoglobin ≥ 9.0 g/dl; Note: The use of transfusion or other intervention to achieve Hgb ≥ 9.0 g/dl is acceptable.

Adequate renal function as follows:

Serum creatinine ≤ 1.5 mg/dl or creatinine clearance (CC) ≥ 50 ml/min determined by 24-hour collection or estimated by Cockcroft-Gault formula:

$$\text{CCr male} = \frac{[(140 - \text{age}) \times (\text{wt in kg})]}{[(\text{Serum Cr mg/dl}) \times (72)]}$$

$$\text{CCr female} = 0.85 \times (\text{CrCl male}).$$

Adequate hepatic function as follows:

Total bilirubin ≤ 1.5 x ULN (except patients with Gilbert Syndrome who can have total bilirubin < 3.0 mg/dL);

AST or ALT ≤ 3 x the upper limit of normal.

Negative serum pregnancy test for women of childbearing potential and confirmation within 24 hours of first dose of study drug.

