3.2 Exclusion Criteria

Presence of distant metastases;

Less than six-month disease free interval from end of prior radiotherapy to the head and neck;

Prior receipt of anti-PD-1/L1 therapy.

Patients who are pregnant or breast feeding;

Clinically significant uncontrolled major cardiac, respiratory, renal, hepatic, gastrointestinal or hematologic disease but not limited to:

Symptomatic congestive heart failure, unstable angina, or cardiac dysrhythmia not controlled by pacer device; myocardial infarction within 3 months of registration.

[figure not shown]
Active autoimmune disorder or immunosuppression (including HIV, but excluding endocrine abnormalities that are controlled with replacement medications);

Active viral hepatitis;

Steroid therapy of greater than prednisone 10 mgs a day or equivalent;

Prior history of invasive non-head and neck cancer within two years, with the exception of screen detected prostate cancer treated with observation only, basal cell and squamous cell carcinoma of the skin, and micro-invasive resected cervical carcinoma.

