6.2.2 Dosage and Administration

A cycle is defined as 28 days with M7824 administered on days 1 and 15.

Participants will receive an IV infusion of M7824 at a dose of 1200 mg over 1 hour (-10 minutes/+20 minutes, ie, over 50 to 80 minutes) on days 1 and 15.

Modifications of the infusion rate due to infusion-related reactions (IRRs) are described in Section 6.2.3. In order to mitigate potential IRRs, premedication with an antihistamine and with acetaminophen approximately 30 to 60 minutes prior to each dose of M7824 is mandatory for the first 2 infusions. Premedication is optional and at the discretion of the Investigator after the second infusion. If Grade \geq 2 infusion reactions are seen during the first 2 infusions, then premedication should not be stopped. Steroids as premedication are not permitted. Special precautions for monitoring of participants and management of IRRs/hypersensitivity, including modifications of the infusion rate and stopping of study drug are described in Section 6.2.3.

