8. CRITERIA FOR SUBJECT WITHDRAWAL

8.1 Withdrawal from Trial Therapy

Participants will be withdrawn from treatment for any of the following reasons:

1. Participants meeting the definition of PD while on treatment based on RECIST or RECIST 1:1 with the exception that participant may continue past PD if the ECOG PS has remained stable, and if in the opinion of the Investigator, the participant will benefit from continued treatment.
2. In case of premature withdrawal from the study treatment for reasons other than PD, the participants will be asked to attend scheduled visits, including tumor assessment and other assessments as planned until PD and end of study or death.
3. Significant clinical deterioration (clinical progression), defined as new symptoms that are deemed by the Investigator to be clinically significant or significant worsening of existing symptoms.
4. Therapeutic failure requiring urgent additional or alternative anticancer treatment.
5. Occurrence of AEs resulting in the permanent discontinuation of the study treatment being desired or considered necessary by the Investigator and/or the participant.
6. Occurrence of pregnancy in the participant.
7. Use of a prohibited concomitant drug, as defined in Section 9.1, where the predefined consequence is withdrawal from the study treatment if considered necessary by the Investigator or the Supporting company EMD Serono.
8. Noncompliance.

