8.4 Definition of End of Study

If the study is not terminated for a reason given in Sections 8.1, 8.2 or 8.3, the end of the study is defined as 1 year after the last participant receives the last dose of M7824.

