Embryo fetal toxicities

Embryo fetal toxicities are a known risk of the PD-1/PD-L1 targeting class. Animal models link the PD-1/PD-L1 signaling pathway with maintenance of pregnancy through induction of maternal immune tolerance to fetal tissue (Guleria, 2005; Leber 2010; Wafula, 2009; Zenclussen 2013). Embryofetal and reproductive toxicities have also been investigated in animal models for a humanized mAb targeting TGF- β 1. At a dose as high as 30 mg/kg, no maternal reproductive toxicity or embryofetal lethality was observed (Hilbush 2016).

Respective safety measures comprise inclusion/exclusion criteria for participation in clinical studies with M7824, guidance for prevention, monitoring, and medical management of potential risks, as well as guidance on study treatment interruption or discontinuation.

Methods of AESI recording and reporting will follow the guideline for AE recording and reporting. Refer to the Investigator Brochure for reporting the identified risks.

Embryo fetal toxicity is an important potential risk of M7824. An appropriate contraception warning is provided as part of inclusion criteria. Pregnant and breastfeeding women are not allowed in the M7824 study and adequate contraceptive measures are recommended during the study to minimize or eliminate the potential risk to the developing fetus.

Functional and patient reported outcomes include but are not limited to:

- Validated clinical grading criteria (Head and Neck-Lymphedema and Fibrosis, HN-LEF)
- Patient-reported measures of head and neck fibrosis (Lymphedema Symptom Inventory Distress Scale, L-SIDS)³
- Radiographic dysphagia grade (Dynamic Imaging Grade of Swallowing Toxicity, DIGEST)
- Cervical range of motion (CROM).

Biomarker Assessments

Due to limited understanding of the biological activities induced by M7824 and radiation in cancer subjects, biomarker assessment will be conducted to examine if the doses are associated with relevant antitumor immune activities. As part of the translational work, this trial will serve to:

1. Evaluate PD-L1 expression as a predictor of response
2. Evaluate the effect on TGF β concentrations in plasma.
3. Evaluate potential predictive / prognostic biomarker candidates related to the drug and / or the cancer (such immune infiltrating populations, tumor mutational burden, systemic cytokine profiles)
 - a. Pancancer Immune Profiling Formalin-Fixed Paraffin-Embedded (FFPE) based assay using Nanostring or HTG technology.

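### Section 10.2 says the inclusion criteria carry a contraception warning, but 3.1 has none, and the supplied protocol text only recommends contraception

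*Combined protocol and SAP*

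**What the plan says.** Section 10.2, under embryo-fetal toxicities, states the risk: "Embryo fetal toxicity is an important potential risk of M7824". It also describes such toxicity as a known risk of the PD-1/PD-L1 class. It names the eligibility criteria among the safety measures and then says: "An appropriate contraception warning is provided as part of inclusion criteria". It adds that "adequate contraceptive measures are recommended during the study to minimize or eliminate the potential risk to the developing fetus".

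The eligibility sections read as follows on reproduction:

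- 3.1 Inclusion Criteria: "Negative serum pregnancy test for women of childbearing potential and confirmation within 24 hours of first dose of study drug".
- 3.2 Exclusion Criteria: "Patients who are pregnant or breast feeding".

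Elsewhere, Table 1 schedules pregnancy tests at screening, every 3 months on treatment, and as clinically indicated in follow-up. Section 8.1 lists "Occurrence of pregnancy in the participant" among the reasons for stopping trial therapy.

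**The concern.** A safety section relies on an eligibility safeguard that the eligibility section does not contain. Someone who reads only 10.2 would believe that contraception is dealt with at entry. Someone who screens a patient against 3.1 would find nothing to act on.

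At stake is who may be dosed with a drug for which the protocol itself records an embryo-fetal risk. If contraception is not addressed at entry, the protocol text leaves prevention to a recommendation in a later section, which is not part of the screening check.

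**Working it through.** No formula or planned figure is involved, so the check sets the relevant sections side by side.

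1. **Where 10.2 points.** It points to the inclusion criteria, which are section 3.1. It does not point to the exclusion criteria, the consent form or the Investigator's Brochure.

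2. **What 3.1 contains.** The list runs from histology to the pregnancy test with no visible gap or redaction. Contraception statements in 3.1: 0. A pregnancy test shows status on the day it is taken. It neither warns about contraception nor asks for it.

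3. **Whether 3.2 could hold the item.** Contraception statements in the readable text of 3.2: 0. One figure in that section could not be read, but it lies in the exclusion list, between the cardiac and autoimmune items. It cannot explain an item missing from 3.1.

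4. **Contraception elsewhere in the supplied text.** There are two statements, both in 10.2: the cross-reference and the recommendation. The pregnancy-testing entry and notes of Table 1 and the withdrawal rule in 8.1 add none.

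5. **What the other measures do.**

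| Measure | Section | Function |
|---|---|---|
| Negative test before first dose | 3.1 | Detects an existing pregnancy |
| Exclusion if pregnant or breast feeding | 3.2 | Acts on a known pregnancy |
| Tests every 3 months on treatment | Table 1 | Detects a pregnancy after dosing has begun |
| Stopping therapy on pregnancy | 8.1 | Responds to a pregnancy |
| Contraceptive measures | 10.2 | Prevents, but is only recommended |

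The one preventive measure in the table is not a condition of entry.

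6. **How long the recommendation runs.** It applies during the study, and under 8.4 "the end of the study is defined as 1 year after the last participant receives the last dose of M7824", unless the study is terminated earlier. For a woman who stays on study, the recommendation therefore extends at least 1 year past her own last dose. The question is its strength and its place in the protocol, not a missing end date. Any new wording should not cut it short.

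**The case against.** The strongest case on the other side has four parts.

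- **10.2 promises a warning, not a requirement.** A reader might infer that the plan meant contraception to be mandatory and that the criterion was lost. The documents do not support that. The cross-reference speaks of a warning, and 10.2 goes on to say that contraception is recommended. This stands: the mismatch is cured once the warning is in 3.1, and a mandatory criterion is a further step that has to be argued on its merits.

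- **The consent pages may already instruct participants.** A reader might infer that women will be treated with no contraception advice. That cannot be concluded, because the consent pages were removed from the supplied text and the Brochure was not supplied. This also stands, and it limits the eligibility consequence to 3.1 and 3.2 read alone. It does not rescue the cross-reference, because consent wording is not an inclusion criterion.

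- **Other safeguards exist.** Besides testing, exclusion and stopping rules, 8.2 lets the investigator withdraw a participant for safety or compliance reasons. These are real protections, but none requires that pregnancy be prevented.

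- **The risk may be modest.** Section 10.2 reports that an antibody to TGF-β1, at doses up to 30 mg/kg, caused no maternal reproductive toxicity or embryofetal lethality in animals. The same section nevertheless attributes the risk to the PD-1/PD-L1 class and keeps it as an important potential risk for M7824.

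**Conclusion.** The statement in 10.2 is wrong as written: the inclusion criteria contain no contraception warning. This is an internal inconsistency with a participant-safety consequence. Judged on 3.1 and 3.2 alone, a woman of childbearing potential who declines contraception is eligible for treatment.

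The size cannot be put as a number. The documents do not say how many women of childbearing potential are expected, and the trial is small (8 patients in the lead-in and a phase II sample size of 21 in section 13.5). The primary endpoint, sample size and analysis are unaffected, so the point is minor.

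The conclusion rests on two assumptions: that the 3.1 list as supplied is complete, and that the unseen consent pages and Brochure do not alter the eligibility criteria.

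**What to change.** **Minimum:** put the contraception warning that 10.2 describes into 3.1.

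**Preferred:** add to 3.1: *Women of childbearing potential must agree to use highly effective contraception during M7824 treatment and for the post-dose period given in the Investigator's Brochure.* Then align 10.2, for example: *Contraception is required as stated in 3.1 and remains recommended for the rest of the study.* The second clause keeps the present recommendation in force where the required period ends sooner. The supplied documents give no post-dose period, so it has to come from the Brochure. The consent form should be checked and matched if needed.

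**Cost:** one inclusion criterion, one sentence in 10.2, and possibly a line in the consent form. No test or visit is added. The downside of the preferred version is that a woman who will not use contraception becomes ineligible; the minimum version excludes no one.

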11. PHARMACOKINETICS

Samples for PK and ADA will be collected according to the Schedule of Assessments in Table 1.

The following PK parameters will be estimated and reported in the PK Analysis Set:

- Ceoi
- Ctrough
- Blood samples of approximately 3.5 mL will be collected for measurement of serum concentrations of M7824, as specified in the Schedule of Assessments. Instructions for the collection and handling of biological samples will be provided by the Supporting company EMD Serono. The actual date and time (24-hour clock time) of each sample will be recorded.
- Samples will be used to evaluate the PK of M7824. Each serum sample will be divided into 2 aliquots (1 each for PK and a back up). Samples collected for analyses of M7824 serum concentration may also be used to evaluate safety or efficacy aspects related to concerns arising during or after the study.

The PK parameters will be summarized using descriptive statistics. Individual as well as mean concentration-time plots will be depicted. Unresolved missing data may be imputed when the analysis integrity is affected. The conservative principle will be used for data imputation.

Table 5 **Pharmacokinetic Parameters**

Symbol	Definition
C_{eo}	The concentration observed immediately at the end of infusion
C_{trough}	The concentration observed immediately before next dosing (corresponding to pre-dose or trough concentration for multiple dosing)

PK and ADA samples collected at the same time points may be used interchangeably if the dedicated sample has insufficient quantity as the participants will have consented to all collections and tests.

PK sampling:

Prior to infusion and immediately after infusion: cycle 1, day 1 and cycle 3 day 1

Prior to infusion cycle 2 day 1 and cycle 6 day 1 OR end of treatment (whatever comes first) and follow-up visit.

ADA sampling:
Prior to infusion cycle 1 day 1 and cycle 6 day 1 or end of treatment (whatever comes first) and follow-up visit.

12. ADVERSE EVENTS

The investigator is required to report to the supporting company EMD Serono or its representative all AEs occurring during the clinical study (Title 21 Code of Federal Regulations [CFR] Part 312.64[b] and International Conference on Harmonization [ICH] E6 [R2]).

At each study visit, subjects will be evaluated for new Adverse Events (AE) and the status of existing AEs. All AEs observed from the date of the first administration of study treatment until the end of the follow-up period of the study (study cut-off date) are to be recorded on the AE page of the e-CRF. The date of onset and resolution, determination of seriousness, severity, grade, corrective treatment, outcome, and relationship to study treatment (M7824, Radiotherapy) will be recorded for all AEs.

All Serious Adverse Events (SAEs) occurring from the date of onset of the study treatment until the end of follow-up period of the study (study cut-off date) will be collected.

This study will utilize the NCI Common Terminology Criteria for Adverse Events (CTCAE) version 5.0 for adverse event (AE) reporting. The CTCAE version 5.0 is located on the CTEP website at http://ctep.cancer.gov/protocolDevelopment/electronic_applications/ctc.htm.

An Adverse Event is defined as any untoward medical occurrence in a patient regardless of its causal relationship to study treatment. An AE can be any unfavorable and unintended sign (including any clinically significant abnormal laboratory test result), symptom, or disease temporally associated with the use of the study treatment, whether or not it is considered to be study drug(s) related. Included in

this definition are any newly occurring events and any previous condition that has increased in severity or frequency since the administration of study therapy.

The investigator (or physician designee) is responsible for verifying and providing source documentation for all adverse events and assigning the attribution for all adverse events for subjects enrolled.

Serious Adverse Events (SAEs) will be reported within 24 hours of acknowledge by the study team, unless it occurs over the weekend or holidays, when it will be notified in the first business day. They are defined as any adverse drug event (experience) occurring at any dose that results in any of the following outcomes: death; a life-threatening adverse drug experience; inpatient hospitalization or prolongation of existing hospitalization; a persistent or significant disability/incapacity; a congenital anomaly/birth defect. Important medical events that may not result in death, be life threatening, or require hospitalization may be considered an SAE, when, based upon medical judgment, they may jeopardize the patient and may require medical or surgical intervention to prevent one of the outcomes listed in the definition.

Toxicities will be assessed by the treating physician/s according to the CT Cv5 criteria.

Early onset (acute) toxicities occurring prior to 90 days will also be considered late onset (chronic) toxicities if they persist for at least one day beyond the 90 days used to define late onset (chronic) toxicities. In analyses that examine acute and chronic toxicities separately, those toxicities that began as acute but became chronic will be included in both the analysis of acute toxicities and in the analysis of chronic toxicities.

Immune-related AEs should be documented as an 'Adverse Event of Special Interest (AESI)', and it is recommended to involve the Medical Monitor at first incidence and subsequently as needed for follow up. Details of the diagnostic work up will be requested by the study team. Immune-related AEs are described in Section 0.

For reporting irAE severity/toxicity grading, refer to NCI-CTCAE v.5 toxicity grading system.

Toxicities related to radiation therapy include: Pain, mucositis, constipation, dysphagia, odynophagia, hemoptysis, epistaxis, trismus, fatigue, weight loss, dysgeusia, nausea, radiation dermatitis, myelosuppression, skin erythema, subcutaneous fibrosis, esophagitis, myelitis, superficial soft tissue fibrosis and esophageal stricture.

Toxicities related to IO therapy are described in detail in the investigator's brochure.

Toxicity monitoring: Both Acute (From radiation start to 90 days after completion of radiation therapy) and Late (90 days to 2 years from the completion of radiation therapy) side effects of radiation therapy will be documented and graded according to the NCI-CTCAE version 5.0.

Table 6: Adverse Event Recording Guidelines**Recommended Adverse Event Recording Guidelines**

Attribution	Grade 1	Grade 2	Grade 3	Grade 4	Grade 5
Unrelated	Phase I	Phase I	Phase I Phase II Phase III	Phase I Phase II Phase III	Phase I Phase II Phase III
Unlikely	Phase I	Phase I	Phase I Phase II Phase III	Phase I Phase II Phase III	Phase I Phase II Phase III
Possible	Phase I Phase II Phase III				
Probable	Phase I Phase II Phase III				
Definitive	Phase I Phase II Phase III				

Serious Adverse Event (SAE) Reporting

An adverse event or suspected adverse reaction is considered “serious” if, in the view of either the investigator or the sponsor, it results in any of the following outcomes:

- Death
- A life-threatening adverse drug experience – any adverse experience that places the patient, in the view of the initial reporter, at immediate risk of death from the adverse experience as it occurred. It does not include an adverse experience that, had it occurred in a more severe form, might have caused death.
- Inpatient hospitalization or prolongation of existing hospitalization
- A persistent or significant incapacity or substantial disruption of the ability to conduct normal life functions.
- A congenital anomaly/birth defect.

Important medical events that may not result in death, be life-threatening, or require hospitalization may be considered a serious adverse drug experience when, based upon appropriate medical judgment, they may jeopardize the patient or subject and may require medical or surgical intervention to prevent one of the outcomes listed in this definition. Examples of such medical events include allergic bronchospasm requiring intensive treatment in an emergency room or at home, blood dyscrasias or convulsions that do not result in inpatient hospitalization, or the development of drug dependency or drug abuse (21 CFR 312.32).

- Important medical events as defined above, may also be considered serious adverse events. Any important medical event can and should be reported as an SAE if deemed appropriate by the Principal Investigator or the IND Sponsor, IND Office.

- All events occurring during the conduct of a protocol and meeting the definition of a SAE must be reported to the IRB in accordance with the timeframes and procedures outlined in "The University of Texas M. D. Anderson Cancer Center Institutional Review Board Policy for Investigators on Reporting Serious Unanticipated Adverse Events for Drugs and Devices". Unless stated otherwise in the protocol, all SAEs, expected or unexpected, must be reported to the IND Office, regardless of attribution (within 5 working days of knowledge of the event).
- **All life-threatening or fatal events**, that are unexpected, and related to the study drug, must have a written report submitted within **24 hours** (next working day) of knowledge of the event to the Safety Project Manager in the IND Office.
- Unless otherwise noted, the electronic SAE application (eSAE) will be utilized for safety reporting to the IND Office and MDACC IRB.
- Serious adverse events will be captured from the time of the first protocol-specific intervention, until 90 days after the last dose of drug, unless the participant withdraws consent. Serious adverse events must be followed until clinical recovery is complete and laboratory tests have returned to baseline, progression of the event has stabilized, or there has been acceptable resolution of the event.
- Additionally, any serious adverse events that occur after the 90 day time period that are related to the study treatment must be reported to the IND Office. This may include the development of a secondary malignancy.

Reporting to FDA:

- Serious adverse events will be forwarded to FDA by the IND Sponsor (Safety Project Manager IND Office) according to 21 CFR 312.32.

It is the responsibility of the PI and the research team to ensure serious adverse events are reported according to the Code of Federal Regulations, Good Clinical Practices, the protocol guidelines, the sponsor's guidelines, and Institutional Review Board policy.

SAEs, whether related or not related to study drug, must be reported to EMD Serono within 24 hours. SAEs must be recorded on BMS approved form.

If only limited information is initially available, follow-up reports are required. (Note: Follow-up SAE reports should include the same investigator term(s) initially reported.)

If an ongoing SAE changes in its intensity or relationship to study drug or if new information becomes available, a follow-up SAE report should be sent within 24 hours to the EMD Serono (or designee) using the same procedure used for transmitting the initial SAE report.

All SAEs should be followed to resolution or stabilization.

The principal investigator will ensure that all SAEs in the clinical database are reported to EMD Serono and any applicable health authority during the conduct of the study.

SAEs will be reported on MDACC IRB approved form for prompt reporting (full form):

“Internal SAE Report Form for Prompt Reporting” Institutional Review Board.

SAEs will be submitted to both the Office of Protocol Research, Unit 1437 at The University of Texas MD Anderson Cancer Center and also sent to MEDWATCH

All SAEs should simultaneously be faxed or e-mailed to EMD Serono.

An SAE report should be completed for any event where doubt exists regarding its seriousness.

Definition of Dose Limiting Toxicity (DLT)

DLT for the combination of SBRT and M7824 in patients with recurrent HNSCC will be defined as:

1. Any \geq grade 3 AE resulting in inability to complete radiotherapy due to toxicity related to M7824 or the combination of M7824 and SBRT.

Drug destruction

Normal saline solution may be disposed of according to local site procedures. Other items used in the dose preparation and administration should be disposed of according to local site procedures.

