13.4 Secondary Endpoints

- The study secondary endpoints include: Overall response rate by RECIST or RECIST 1:1

- 1- year locoregional control (LRC), locoregional failure free survival (LFFS), distant metastasis (DM) and overall survival (OS) rates
- Acute and late toxicity accessed by the Common Terminology Criteria for Adverse Events (CTCAE)-5.0
- Fibrosis-related toxicities/functional outcomes
- Patient Reported Outcome (PRO) measures of symptoms using MD Anderson Symptom Inventory (MDASI).
- Volumetric tumor regression rate and MRI kinetic biomarkers after M7824 plus SBRT therapy
- Quality-Adjusted-Life-Years (QALY) between M7824 plus SBRT reirradiation and historic SBRT reirradiation control

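### Section 12 requires every adverse event to be recorded, but Table 6 lists grade 1-2 unrelated or unlikely events for Phase I only, and nothing says which rule governs this phase I/II trial

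*Combined protocol and SAP*

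**What the plan says.** The text of Section 12 sets a rule without exceptions. It requires that "All AEs observed from the date of the first administration of study treatment until the end of the follow-up period" be entered on the adverse event page of the e-CRF, with relationship to study treatment among the items kept for each event. The investigator must report to the supporting company "all AEs occurring during the clinical study". An adverse event is defined as "any untoward medical occurrence in a patient regardless of its causal relationship to study treatment", so a low causality rating does not take an event out of scope.

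Table 6, later in the same section, is headed "Recommended Adverse Event Recording Guidelines". It crosses attribution with grade and shows in each cell the trial phases in which such an event is recorded. Two rows matter here. The first begins "Unrelated Phase I Phase I Phase I Phase II Phase III" and the second "Unlikely Phase I Phase I Phase I Phase II Phase III". In both, the cells for grades 1 and 2 hold Phase I alone, and Phase II appears only from grade 3.

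Section 13.4 makes toxicity a secondary endpoint: "Acute and late toxicity accessed by the Common Terminology Criteria for Adverse Events (CTCAE)-5.0". It states no restriction by attribution.

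**The concern.** The text and the table give different instructions for the same event in the same trial. A grade 2 event rated unlikely in a phase II patient must be recorded under the text, and is left out under the table. No sentence ranks one above the other or says which Table 6 label applies to which patients.

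Applying the table by part is a natural reading, because the protocol uses the table's own labels for its parts. Section 13.2 speaks of Phase I and Phase II parts, Section 13.5 of phase I and phase II portions, and Section 13.6 sets separate toxicity-summary schedules for the two.

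At stake is the all-cause low-grade part of the CTCAE secondary endpoint. A site that follows the table by part would capture these events for the lead-in patients and filter them for later patients. The filter would depend on an attribution made by an unblinded investigator in a trial with no control arm, where causality is hard to judge. An event never entered cannot easily be re-attributed later. The toxicity summaries that Section 13.6 requires after the lead-in, and then after every 3 evaluable phase II patients, would rest on different capture rules.

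**Working it through.** The plan gives no figure on this point to reproduce. The check sets the two rules side by side and then counts the patients to whom the difference could apply.

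**1. The two rules for a phase II patient**

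| Event | Section 12 text | Table 6, Phase II |
|---|---|---|
| Grade 1-2, unrelated or unlikely | recorded | not listed |
| Grade 3 or higher, unrelated or unlikely | recorded | listed |
| Possible, probable or definitive | recorded | listed |

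The last row rests on the entries visible in the extracted table. Each of those three rows shows one entry naming Phases I, II and III, which I take to span all grades. The conflict is confined to the first row.

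**2. Patients exposed if Table 6 is applied by part**

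Inputs from Section 13.5: 8 lead-in patients and a phase II sample size of 21. The section does not say whether the 21 include the 8.

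Share exposed = (N − 8)/N, where N is the total enrolled.

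- 21 include the lead-in: (21 − 8)/21 = 13/21 = 62%.
- 21 are additional: N = 8 + 21 = 29, and 21/29 = 72%.

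At the stated accrual of 2 patients per month, 21 patients take 10.5 months and 29 take 14.5. The stated 11 months fits 21 in total better, but does not settle it.

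**3. Possible loss among all grade 1-2 events**

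The documents do not give the share r of grade 1-2 events that will be rated possible or higher, so I assume a range. I also assume the same number of low-grade events per patient, and the same attribution split, in both parts.

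Fraction of pooled grade 1-2 events not recorded = (1 − r) × (N − 8)/N.

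| Assumed r | N = 21 | N = 29 |
|---|---|---|
| 20% | 0.80 × 0.619 = 50% | 0.80 × 0.724 = 58% |
| 50% | 0.50 × 0.619 = 31% | 0.50 × 0.724 = 36% |
| 80% | 0.20 × 0.619 = 12% | 0.20 × 0.724 = 14% |

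Among events rated possible or higher the loss is 0. If the Section 12 text governs, the loss is 0 in every cell.

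**4. What is outside the conflict**

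The adverse-event criterion for a dose-limiting toxicity, in Section 12 and in Section 13.5, needs grade 3 or higher and a relation to M7824 or the combination. Such events are listed for every phase in Table 6. The lead-in rule of Section 13.2 therefore stands, and its figures reproduce by exact binomial: P(3 or more of 8 | 0.5) = 219/256 = 0.855 against the stated 0.86, and P(2 or fewer of 8 | 0.2) = 0.797 against the stated 80%.

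**The case against.** The strongest reply is that the text is mandatory and the table only recommended. Table 6 has Phase III entries although this trial has no phase III, so it looks like a general template that was never meant to limit the text. A phase I/II trial could also be run under the Phase I entries throughout. On either view nothing is lost. This stands as an argument about how large the consequence is. It does not remove the contradiction: the table is the only grid by grade and attribution in the section, staff may well use it, and no sentence tells them not to.

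A reader might infer that low-grade toxicity will be undercounted. The documents do not support that as a flat statement. Any loss depends on sites applying the table by part, and even then events attributed to treatment as possible or higher are kept.

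A reader might also infer that the fibrosis endpoint is biased, because every patient has had earlier radiation to which new changes could be attributed. That goes too far. Section 12 names fibrosis, dysphagia and trismus among radiation toxicities, and requires acute and late radiation effects to be documented and graded, with no grade floor. Fibrosis and function are also measured on a schedule by HN-LEF, CROM, DIGEST and patient-reported instruments (Table 1, Section 5.1), which do not pass through adverse event attribution. The documents give no rate from which a fibrosis shortfall could be computed.

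Nor does the anemia event of special interest suffer by definition: Section 10.2 limits it to treatment-related anemia. Finally, Section 13.6 plans no formal comparison of lead-in with phase II toxicity, so non-comparability affects how the summaries are read, not a planned test.

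**Conclusion.** This is an internal contradiction. Two recording rules stand in Section 12, they differ for grade 1-2 events rated unrelated or unlikely in Phase II, and the protocol does not say which governs. That much is certain from the wording.

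The consequence is conditional. If Table 6 is applied by part, all-cause low-grade events may be under-recorded in 62% or 72% of patients, depending on whether the 21 include the lead-in, and would not be comparable with the 8 lead-in patients. These percentages count patients under the narrower rule, not patients with a lost event. The share of low-grade events lost cannot be derived from the documents; the 12% to 58% range above rests on assumed attribution splits and equal event rates in both parts. The point touches the all-cause low-grade part of one secondary endpoint. It does not touch the primary endpoint or the safety stopping rule. It should still be corrected before enrollment, because events that were never recorded may not be recoverable.

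**What to change.** State in Section 12 that the text governs, and delete Table 6 or change its unrelated and unlikely rows to agree with it, so that all grades and all attributions are recorded for every patient in both parts. Attribution is already kept for each event, so treatment-related summaries can still be produced at the analysis stage.

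The cost is one edit to the protocol and some additional low-grade entries for the 13 to 21 phase II patients. The correction itself adds no visits or assessments.
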